thrombocytopenia. Hemolysis reported in individuals with glucose-6-phosphate dehydrogenase (G-6-PD) deficiency.

Cardiac Disorders: Cardiomyopathy which may result in cardiac failure and in some cases a fatal outcome (see WARNINGS and OVERDOSAGE). Hydroxychloroquine sulfate tablets prolong the QT interval. Ventricular arrhythmias and torsade de pointes have been reported in patients taking hydroxychloroquine sulfate tablets (see OVERDOSAGE and DRUG INTERACTIONS).

Ear and Labyrinth Disorders: Vertigo, tinnitus, nystagmus, nerve deafness, deafness.

Eye Disorders: Irreversible retinopathy with retinal pigmentation changes (bull's eye appearance), visual field defects (paracentral scotomas) and visual disturbances (visual acuity), maculopathies (macular degeneration), decreased dark adaptation, color vision abnormalities, corneal changes (edema and opacities) including corneal deposition of drug with or without accompanying symptoms (halo around lights, photophobia, blurred vision).

Gastrointestinal Disorders: Nausea, vomiting, diarrhea, and abdominal pain.

General Disorders and Administration Site Conditions: Fatigue.

Hepatobiliary Disorders: Liver function tests abnormal, hepatic failure acute.

Immune System Disorders: Urticaria, angioedema, bronchospasm.

Metabolism and Nutrition Disorders: Decreased appetite, hypoglycemia, porphyria, weight decreased.

Musculoskeletal and Connective Tissue Disorders: Sensorimotor disorder, skeletal muscle myopathy or neuropathy leading to progressive weakness and atrophy of proximal muscle groups, depression of tendon reflexes and abnormal nerve conduction.

Nervous System Disorders: Headache, dizziness, seizure, ataxia and extrapyramidal disorders such as dystonia, dyskinesia, and tremor have been reported with this class of drugs.

Psychiatric Disorders: Affect/emotional lability, nervousness, irritability, nightmares, psychosis, suicidal behavior.

Skin and Subcutaneous Tissue Disorders: Rash, pruritus, pigmentation disorders in skin and mucous membranes, hair color changes, alopecia. Dermatitis bullosa eruptions including erythema multiforme, Stevens-Johnson Syndrome, and toxic epidermal necrolysis, drug reaction with eosinophilia and systemic symptoms (DRESS syndrome), photosensitivity, dermatitis exfoliative, acute generalized exanthematous pustulosis (AGEP). AGEP has to be distinguished from psoriasis, although hydroxychloroquine sulfate tablets may precipitate attacks of psoriasis. It may be associated with pyrexia and hyperleukocytosis.

To report SUSPECTED ADVERSE REACTIONS, contact Mylan Pharmaceuticals Inc. at [name] ([name]) or FDA at [name] or www.fda.gov/medwatch.

OVERDOSAGE: The 4-aminoquinoline compounds are very rapidly and completely absorbed after ingestion, and in accidental overdosage, or rarely with lower doses in hypersensitive patients, toxic symptoms may occur within 30 minutes. The symptoms of overdosage may include headache, drowsiness, visual disturbances, cardiovascular collapse, convulsions, hypokalemia, rhythm and conduction disorders including QT prolongation, torsades de pointes, ventricular tachycardia and ventricular fibrillation, followed by sudden potentially fatal respiratory and cardiac arrest. Treatment is symptomatic and must be prompt. Immediate gastric lavage until the stomach is completely emptied is indicated. After lavage, activated charcoal is introduced by the stomach tube within 30 minutes of ingestion of the drug may inhibit further intestinal absorption. To be effective, the dose of activated charcoal should be at least five times the estimated dose of hydroxychloroquine ingested.

Consideration should be given to administering diazepam parenterally since studies suggest that it may be beneficial in reversing chloroquine and hydroxychloroquine cardiotoxicity.

Respiratory support and shock management should be instituted as necessary.

Exchange transfusions are used to reduce the level of 4-aminoquinoline drug in the blood.

A patient who survives the acute phase and is asymptomatic should be closely observed for at least six hours. Fluids may be forced and sufficient ammonium chloride (8 g daily in divided doses for adults) may be administered for a few days to acidify the urine. This will promote urinary excretion in cases of both overdosage and sensitivity. However, caution must be exercised in patients with impaired renal function and/or metabolic acidosis.

DOSAGE AND ADMINISTRATION: One hydroxychloroquine sulfate tablet contains 200 mg of hydroxychloroquine sulfate, which is equivalent to 155 mg base.

Take hydroxychloroquine sulfate tablets with a meal or a glass

of milk.

Malaria: Prophylaxis: Adults: 400 mg (310 mg base) once weekly on the same day of each week starting 2 weeks prior to exposure, and continued for 4 weeks after leaving the endemic area.

Weight-Based Dosing in Adults and Pediatric Patients: 6.5 mg/kg (5 mg/kg base), not to exceed 400 mg (310 mg base), once weekly on the same day of the week starting 2 weeks prior to exposure, and continued for 4 weeks after leaving the endemic area.

Treatment of Uncomplicated Malaria: Adults: 800 mg (620 mg base) followed by 400 mg (310 mg base) at 6 hours, 24 hours and 48 hours after the initial dose (total 2000 mg hydroxychloroquine sulfate or 1550 mg base).

Weight Based Dosage in Adults and Pediatric Patients: 13 mg/kg (10 mg/kg base), not to exceed 800 mg (620 mg base) followed by 6.5 mg/kg (5 mg/kg base), not to exceed 400 mg (310 mg base), at 6 hours, 24 hours and 48 hours after the initial dose. Hydroxychloroquine sulfate tablets film-coated tablets cannot be divided, therefore they should not be used to treat patients who weigh less than 31 kg.

For radical cure of *P. vivax* and *P. malariae* infections, concomitant therapy with an 8-aminoquinoline compound is necessary.

Lupus Erythematosus: The recommended adult dosage is 200 mg to 400 mg (155 mg to 310 mg base) daily, administered as a single daily dose or in two divided doses. Doses above 400 mg a day are not recommended.

The incidence of retinopathy has been reported to be higher when this maintenance dose is exceeded.

Rheumatoid Arthritis: The action of hydroxychloroquine is cumulative and may require weeks to months to achieve the maximum therapeutic effect (see CLINICAL PHARMACOLOGY).

Initial Adult Dosage: 400 mg to 600 mg (310 mg to 465 mg base) daily, administered as a single daily dose or in two divided doses. In a small percentage of patients, side effects may require temporary reduction of the initial dosage.

Maintenance Adult Dosage: When a good response is obtained, the dosage may be reduced by 50 percent and continued at a maintenance level of 200 mg to 400 mg (155 mg to 310 mg base) daily, administered as a single daily dose or in two divided doses.

Do not exceed 600 mg or 6.5 mg/kg (5 mg/kg base) per day, whichever is lower, as the incidence of retinopathy has been reported to be higher when this maintenance dose is exceeded.

Corticosteroids and salicylates may be used in conjunction with hydroxychloroquine sulfate tablets, and they can generally be decreased gradually in dosage or eliminated after a maintenance dose of hydroxychloroquine sulfate tablets has been achieved.

HOW SUPPLIED: Hydroxychloroquine Sulfate Tablets, USP are available containing 200 mg of hydroxychloroquine sulfate, USP, equivalent to 155 mg base.

The 200 mg tablets are white, film-coated, round, unscored tablets debossed with **M** on one side of the tablet and **373** on the other side. They are available as follows:

NDC 0378-0373-01
bottles of 100 tablets

Store at 20° to 25°C (68° to 77°F). [See USP Controlled Room Temperature.]

Dispense in a tight, light-resistant container as defined in the USP using a child resistant closure. Keep out of the reach of children.

Do not crush or divide hydroxychloroquine sulfate film-coated tablets (see DOSAGE AND ADMINISTRATION).

Mylan Pharmaceuticals Inc.
Morgantown, WV 26505 U.S.A.

Revised: 2/2017
HXCC.F10

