| | 
 • High-risk person defined by: 
 • Age 18-44 with 2 or more comorbidities listed below • Age 45-79 with any comorbid condition listed below • Age 80 and above (regardless of comorbid conditions) • Co-morbid list 
 ○ Congestive Heart Failure (CHF) ○ Chronic lung disease[‡] ○ Solid organ transplant or immunosuppression* ○ Chronic Kidney Disease or End Stage Renal Disease ○ Diabetes mellitus ○ Cardiovascular disease/Hypertension ○ Smoking/Vaping (currently using or history of using in the past 1 year) ○ Obesity (calculated by height and weight per participant report) ○ Hyperlipidemia ‡Includes any of the following: asthma, chronic obstructive pulmonary disease, emphysema * Defined as an outpatient prescription of greater than 10 mg/day of prednisone or equivalent, use of chemotherapy, or use of immunosuppressive agents for solid organ transplant or for an autoimmune disease. • No current symptoms attributable to COVID-19 • No prior COVID-19 positive diagnosis (eligible if previous testing is negative and meets all other inclusion and exclusion) • Ability to provide informed consent • Confirmed review of concomitant medications (with emphasis on cardiac medications) |
| | 
Exclusion Criteria:
 
Exclusion Criteria Cohort A & B:
 
 • Known allergy to hydroxychloroquine or quinine • Known history of long QT syndrome • Known history of arrhythmia or dysrhythmia • Known current QTc >500 ms • Known G6PD deficiency • Known history of hypoglycemia • Pregnant or Nursing by patient history • Use of any of the following concomitant medications: See Appendix D for Exclusion medication list • Concurrent diagnosis of dermatitis, porphyria, or psoriasis • History of chronic liver disease, including cirrhosis and/or diagnosis of hepatitis (infectious, idiopathic, or immune) • History of chronic kidney disease • Pre-existing retinopathy • Already taking hydroxychloroquine • Any condition or medication in the opinion of the investigator that would prohibit the use of hydroxychloroquine • Enrollment in another clinical with investigational drug or device • Inability to swallow pills • Adults unable to provide informed consent |

| | |
|---------------------------|--|
| | |
| Sample Size | Cohort A n= 1356 Cohort B n= 383 |
| Study Intervention | Hydroxychloroquine vs. Placebo (Vitamin D with calcium) |

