6.0 Study Intervention

6.1 Study Intervention(s) Administered:

Hydroxychloroquine/placebo (vitamin D with calcium) will be administered as part of this study. Randomization will occur at a 1:1 ratio in each cohort. Participation in additional non-interventional clinical research studies is allowed. If the participant becomes infected with COVID-19, the participant will stop the intervention and be treated per the discretion of their primary care provider.

Subjects enrolled will be assigned to the appropriate cohort and randomized to receive hydroxychloroquine 200mg tablets, Day 1 – 2 tablets by mouth twice per day, Day 2-5 1 tablet by mouth twice per day (total of 12 tablets) or placebo. Placebo will be vitamin D with calcium tablets 10mcg tablet - Day 1 – 2 tablets by mouth twice per day, Day 2-5 1 tablet by mouth twice per day (total of 12 tablets). Subjects will be monitored for any toxicities during and after treatment.

Table 2. Intervention dosing

| Drug | Dose | Dose Frequency | Route |
|--|-----------|-------------------------|-------|
| Hydroxychloroquine 200 mg tablets | 2 tablets | Twice daily on day 1 | PO |
| | 1 tablet | Twice daily on days 2-5 | PO |
| Placebo (vitamin D with calcium, 10mcg/25mg tablets) | 2 tablets | Twice daily on day 1 | PO |
| | 1 tablet | Twice daily on days 2-5 | PO |

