6.2.7. Contraindications

Use of hydroxychloroquine sulfate is contraindicated in patients with known hypersensitivity to 4-aminoquinoline compounds. Use with

caution in patients with alcoholism, hepatic/renal dysfunction, glucose-6-phosphate dehydrogenase (G-6-PD) deficiency, gastrointestinal, neurological, or blood disorders. A dose reduction may be required.

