3. Worsening of Psoriasis and Porphyrria: Use of hydroxychloroquine sulfate in patients with psoriasis may precipitate a severe attack of psoriasis. When used in patients with porphyria the condition may be exacerbated. The preparation should not be used in these conditions unless in the judgment of the physician the benefit to the patient outweighs the possible hazard.
4. Proximal Myopathy and Neuropathy: Skeletal muscle myopathy or neuropathy leading to progressive weakness and atrophy of proximal muscle groups, depressed tendon reflexes, and abnormal nerve conduction, have been reported. Muscle and nerve biopsies have been associated with curvilinear bodies and muscle fiber atrophy with vacuolar changes. Assess muscle strength and deep tendon reflexes periodically in patients on long-term therapy with hydroxychloroquine sulfate.
5. Neuropsychiatric Events, Including Suicidality: Suicidal behavior has been rarely reported in patients treated with hydroxychloroquine sulfate.
6. Hypoglycemia: Hydroxychloroquine sulfate has been shown to cause severe hypoglycemia including loss of consciousness that could be life threatening in patients treated with or without antidiabetic medications. Patients treated with hydroxychloroquine sulfate should be warned about the risk of hypoglycemia and the associated clinical signs and symptoms. Patients presenting with clinical symptoms suggestive of hypoglycemia during treatment with hydroxychloroquine sulfate should have their blood glucose checked and treatment reviewed as necessary.
7. Dermatologic Effects: Dermatologic reactions to hydroxychloroquine sulfate may occur and, therefore, proper care should be exercised when it is administered to any patient receiving a drug with a significant tendency to produce dermatitis.

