8.0 Study Procedures and Safety Assessments

8.1 Administrative Procedures

8.1.1 Screening Procedures

All participants must agree to participate in the study prior to any study specific screening procedures being performed. Every participant shall be provided an Institutional Review Board (IRB)-approved informed consent to review and keep for his/her records.

Once consent has been documented, the site will assign the participant a screening number. A Screening Log of consented patients will be maintained at each site.

Screening evaluations will be used to determine the eligibility of the participant for study inclusion. All screening activities must be completed within 48 hours prior to study enrollment and include the following:

- Inclusion/Exclusion Criteria
- Demographics and Medical History

All screening evaluations must be completed and reviewed by the site investigator or healthcare licensed designee to confirm that potential participants meet all eligibility criteria. The study team will maintain a screening log to record details of all participants screened and to confirm eligibility or record reasons for screening failure, as applicable.

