8.1.5 Enrollment

Once all screening procedures have been completed the site PI or licensed designee (RN, CNP, pharmacist, or physician) on the study team will review and acknowledge the inclusion/exclusion source document. If the potential participant is determined to be eligible, the study site will enroll the participant in appropriate cohort in the electronic data capture (EDC) and then randomized by the Sanford Command Core to the intervention assignment. Sites will be notified by email in real time the randomization confirmation. The site study team will maintain an enrollment log and the lead site will maintain a study-wide enrollment log. If the potential participant is not eligible and becomes a screen fail, the reason will be noted on the inclusion/exclusion in the EDC and filed in the study records.

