Drugs that Prolong QT Interval and Other Arrhythmogenic Drugs: Hydroxychloroquine sulfate tablets prolong the QT interval and should not be administered with other drugs that have the potential to induce cardiac arrhythmias. Also, there may be an increased risk of inducing ventricular arrhythmias if hydroxychloroquine sulfate tablets are used concomitantly with other arrhythmogenic drugs.

Mefloquine and Other Drugs Known to Lower the Convulsive Threshold: Hydroxychloroquine sulfate tablets can lower the convulsive threshold. Co-administration of hydroxychloroquine sulfate tablets with other antimalarials known to lower the convulsion threshold (e.g., mefloquine) may increase the risk of convulsions.

Antiepileptic: The activity of antiepileptic drugs might be impaired if co-administered with hydroxychloroquine sulfate tablets.

Methotrexate: Combined use of methotrexate with hydroxychloroquine sulfate tablets have not been studied and may increase the incidence of adverse effects.

Cyclosporin: An increased plasma cyclosporin level was reported when cyclosporin and hydroxychloroquine sulfate tablets were co-administered.

The following interactions have been observed on treatment with the structurally related substance chloroquine phosphate, and therefore cannot be ruled out for hydroxychloroquine.

Praziquantel: Chloroquine has been reported to reduce the bioavailability of praziquantel.

Antacids and Kaolin: Antacids and kaolin can reduce absorption of chloroquine; an interval of at least 4 hours between intake of these agents and chloroquine should be observed.

Cimetidine: Cimetidine can inhibit the metabolism of chloroquine, increasing its plasma level. Concomitant use of cimetidine should be avoided.

Ampicillin: In a study of healthy volunteers, chloroquine significantly reduced the bioavailability of ampicillin.

Information for Patients: Patients should be informed of the early signs and symptoms of toxicity such as rash or visual changes. Patients must see their physicians promptly in case of the appearance of these or of any unusual effects. Periodic laboratory tests may be recommended in some patients. Patients should be fully informed of the potential risks of the use of hydroxychloroquine sulfate tablets, especially in pregnancy and in children.

Carcinogenesis, Mutagenesis, Impairment of Fertility: Long-term studies in animals have not been conducted to evaluate the carcinogenic potential of hydroxychloroquine sulfate tablets.

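### Antiepileptics are the one interaction heading of the Appendix C label that Appendix D does not carry over, and no exclusion names seizure disorder

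*Combined protocol and SAP*

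**What the plan says.** Appendix C reproduces the hydroxychloroquine label. Under Drug Interactions it states that "Hydroxychloroquine sulfate tablets can lower the convulsive threshold" and, under a separate antiepileptic heading, that "The activity of antiepileptic drugs might be impaired if co-administered with hydroxychloroquine sulfate tablets". Its Adverse Reactions section includes seizure among nervous system reactions reported with this class of drugs.

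In the protocol body, Section 6.2.7 advises "caution in patients with alcoholism, hepatic/renal dysfunction, glucose-6-phosphate dehydrogenase (G-6-PD) deficiency, gastrointestinal, neurological, or blood disorders". Section 6.2.9 (Side Effects) does not mention seizure. Its nearest item is "Neuropsychiatric Events, Including Suicidality: Suicidal behavior has been rarely reported in patients treated with hydroxychloroquine sulfate". The heading of Section 6.2 does send the reader to Appendix C for more information.

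Eligibility is set in Section 1.1. One exclusion bars the medications listed in Appendix D. Another, the catch-all, excludes "Any condition or medication in the opinion of the investigator that would prohibit the use of hydroxychloroquine". No exclusion for either cohort names epilepsy or seizure disorder. Section 6.8 adds no barred drugs and refers back to these criteria.

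Screening under Section 8.1.1 covers "Demographics and Medical History" as well as the eligibility criteria. Cohort B also has an inclusion item requiring a confirmed review of concomitant medications, with emphasis on cardiac drugs. Cohort A has no such item.

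**The concern.** The protocol used the label to decide which concomitant drugs to bar, and one interaction did not make it onto the list. Nothing in the documents explains the omission, so it looks more like an oversight than a decision.

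Followed as written, the plan allows a person with epilepsy, or one taking most antiepileptics, to be enrolled unless someone chooses to exclude them. With 1:1 randomisation, half of any such participants would receive a drug that the protocol's own appendix says can lower the convulsive threshold and might weaken their treatment.

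The later safeguards act only once drug has been taken. The Day 3 and Day 5 calls collect adverse events. Under Section 8.3.1, a single serious adverse event judged at least possibly related holds enrolment and convenes the Safety Review Committee. One seizure meeting that description would therefore interrupt the trial as well as harm the participant.

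**Working it through.** **Step 1. Compare the label's interaction headings with Appendix D.** The plan states no figure to reproduce, so the check is a side-by-side reading.

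| Heading in Appendix C, Drug Interactions | What the label says | In Appendix D? |
|---|---|---|
| Digoxin | Monitor serum levels | Yes, short list |
| Insulin or antidiabetic drugs | Lower doses may be needed | Yes, short list |
| QT-prolonging and arrhythmogenic drugs | Should not be given together | Yes, QT list |
| Mefloquine and others lowering the convulsive threshold | May raise convulsion risk | Mefloquine, short list |
| Antiepileptics | Activity might be impaired | Not as a class; felbamate and ezogabine only, via the QT list |
| Methotrexate | Not studied; may increase adverse effects | Yes, short list |
| Cyclosporin | Raised level reported | Yes, short list |
| Praziquantel | Lower bioavailability, seen with chloroquine | Yes, short list |
| Antacids and kaolin | Keep 4 hours apart, from chloroquine data | Yes, short list |
| Cimetidine | Avoid, from chloroquine data | Yes, short list |
| Ampicillin | Lower bioavailability, seen with chloroquine | Yes, short list |

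The short list contains no antiepileptic entry. In the QT list, only ezogabine and felbamate are classed as anticonvulsants. Exclusion criteria naming seizure disorder or epilepsy: none.

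**Step 2. Judge the omission by the protocol's own threshold.** Appendix D bars antacids, for which the label asks only for spacing; digoxin, for which it asks only for monitoring; and ampicillin and praziquantel, on chloroquine findings. The antiepileptic statement concerns hydroxychloroquine itself and is no weaker than these.

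**Step 3. Ask whether the catch-all closes the gap.** It covers what, in the investigator's opinion, would prohibit hydroxychloroquine. The label cautions in neurological disorders and does not forbid use with antiepileptics. An investigator could exclude such a person, or could reasonably conclude that the criterion is not met.

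**Step 4. Illustrate the size.** The documents give no prevalence. Let p be the share of otherwise eligible adults with a known seizure disorder or taking an antiepileptic for seizure control. Assume p = 0.5%, 1% or 2%, and that judgement excludes nobody. Planned enrolment is 1356 + 383 = 1739 (Section 9.2).

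| p | Cohort A: 1356 × p | Cohort B: 383 × p | Total | Half on active drug |
|---|---|---|---|---|
| 0.5% | 6.8 | 1.9 | 8.7 | 4.3 |
| 1% | 13.6 | 3.8 | 17.4 | 8.7 |
| 2% | 27.1 | 7.7 | 34.8 | 17.4 |

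These are people exposed, not expected seizures.

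**Step 5. Screening cost of excluding them.** To enrol N people when a share p is newly ineligible, screen N / (1 − p), rounded up.

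| p | Cohort A | Cohort B | Extra screened |
|---|---|---|---|
| 0.5% | 1363 (+7) | 385 (+2) | 9 |
| 1% | 1370 (+14) | 387 (+4) | 18 |
| 2% | 1384 (+28) | 391 (+8) | 36 |

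**The case against.** The strongest reply is that the label does not ask for this exclusion. Its only contraindication is hypersensitivity to 4-aminoquinolines. On antiepileptics it says activity might be impaired and does not say to avoid the combination, as it does for cimetidine and QT drugs. The convulsive-threshold sentence sits under the mefloquine heading, and mefloquine is barred. All of this stands, and it is why the point is not a breach of the label. It does not explain why Appendix D bars other drugs on no stronger grounds.

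The plan also has routes to exclusion or correction: the catch-all, the Section 6.2.7 caution, the medical history, the Cohort B medication review, the instruction in Section 6.4 to report medication changes, and the investigator's power under Section 7.0 to withdraw someone inappropriately enrolled. These reduce the exposure. None of them requires exclusion.

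Three stronger readings are tempting, and the documents do not support them.

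- A reader might infer that Section 6.2.7, which says a dose reduction may be required, conflicts with the single fixed regimen in Section 6.1. The label ties dose reduction to hepatic or renal disease and to medicines affecting those organs, not to neurological disorders. Chronic liver and kidney disease are already named exclusions.
- A reader might infer that eligibility review is weak because Section 8.1.5 allows a "licensed designee (RN, CNP, pharmacist, or physician) on the study team will review and acknowledge the inclusion/exclusion source document". Every permitted reviewer is licensed, and nothing suggests that a nurse or pharmacist is less reliable on this question.
- A reader might infer that neurological disorders were singled out for lax treatment. Of the seven cautions in Section 6.2.7, three became named exclusions (liver disease, kidney disease, G6PD deficiency). The other four (alcoholism, gastrointestinal, neurological and blood disorders) were all left to judgement. What sets seizure apart is the specific interaction statement, not the general caution.

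Finally, the inclusion/exclusion source document is not among the documents and consent pages were removed, so whether screening staff already ask about seizures cannot be determined.

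**Conclusion.** The gap is real and narrow. Antiepileptics are the only interaction heading in the Appendix C label with no corresponding class or named-drug entry on the Appendix D short list or coverage by the QT list as a whole, and no eligibility criterion names seizure disorder. Exclusion is permitted but not required.

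This is a safety improvement of modest priority. It is not an error, not a breach of a label prohibition, and has no bearing on alpha or power. The illustrative exposure is about 9, 17 or 35 of 1739 participants, with about 4, 9 or 17 on hydroxychloroquine. It rests wholly on the assumed 0.5%, 1% or 2% and on no one being excluded by judgement. Judgement would lower these counts, and the true prevalence could lie outside the range. The harm cannot be sized: no seizure risk is given for a 5-day course, and the label itself says the frequency and causality of its reported reactions cannot always be established reliably.

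**What to change.** Add *Known seizure disorder or epilepsy* to the Cohort A and B exclusion criteria in Section 1.1, and carry it into the inclusion/exclusion source document used at screening. Add *Antiepileptic drugs taken for seizure control* to the Appendix D short list. People taking these drugs for another indication would stay eligible, subject to the existing catch-all, which avoids excluding more people than the concern justifies.

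The cost is one criterion, one list entry, one checklist item and a question about why an antiepileptic is being taken. Slightly fewer people would be eligible. Because screen failures do not count towards enrolment (Section 5.2, Screen Failures), the extra screening worked out above is the only effect on numbers, and the sample sizes in Section 9.2 stand.
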